4.3.2.3. Methods for Hybrid Imputations

For efficacy analyses relative to “treatment-regimen” estimand, missing values resulting from ICEs will be handled as follows:

- Category 1: for missing data solely due to exceptional circumstances, such as pandemic or natural disasters (after other reasons for missing data are ruled out), the analysis will consider the missing data as missing at random. The missing data will be imputed using all nonmissing data of the primary outcome measurement from the same treatment arm.

- Category 2: for missing data due to all other ICEs, missing data will be imputed based on retrieved dropouts in the same treatment arm, defined as observed primary outcome measurements from participants in the same treatment group, who had their efficacy assessed after early discontinuation of the study drug. In cases where there are not enough retrieved dropouts to provide a reliable imputation model (eg, the model implemented by the SAS program does not converge), an alternative multiple imputation method with reference to the placebo group (that is, placebo multiple imputation) will be used.

In cases where placebo multiple imputation method is used for missing data imputation in Category 2 due to not enough retrieved dropouts, the missing data in Category 1 will also be imputed using all nonmissing data of the primary outcome measurement from the placebo group.

4.3.2.4. Sensitivity Analysis Related to Treatment Regimen Estimand

For submission of Study GPHL to the US FDA to support the registration of tirzepatide for chronic weight management, additional sensitivity analyses of the primary efficacy outcomes will be conducted using the FAS and guided by the “treatment-regimen” estimand, which represents the efficacy irrespective of adherence to study drug. This assessment will analyze percent change in body weight obtained at the 72-week visit using an ANCOVA and the percentage of participants achieving at least 5% body weight reduction obtained at the 72-week visit using a logistic regression model. The terms for both models will be the same as specified in Section 4.3.2.1. These analyses are intended to assess the robustness of primary efficacy results using different missing data imputation methods:

- Retrieved dropout multiple imputation: Missing values of change in body weight at the 72-week visit will be imputed based on observed body weight change from baseline values at the visit from participants in the same treatment group who had their efficacy assessed after early discontinuation of study drug. In cases where there are not enough retrieved dropouts to provide a reliable imputation model (for example, the model implemented by the SAS program does not converge), the placebo multiple imputation method (described below) will be used.
- Placebo multiple imputation: Missing values of change in body weight at the 72-week visit will be imputed based on observed body weight change from baseline values at the visit from participants in the placebo treatment group.
- Return to baseline imputation: Missing values of body weight at the 72-week visit will be imputed using the return-to-baseline multiple imputation method to account for within subject variability (Qu et al. 2022).

4.4. Secondary Endpoint(s)/Estimands(s) Analysis

4.4.1. Key Secondary Analyses Subject to Type 1 Error Rate Control

Table GPHL.4.2. Key Secondary Measures (Controlled for Type 1 Error)

Objectives	Relative to the efficacy measure:	Analysis conducted in a manner similar to	Additional Information
Tirzepatide 10 mg and/or 15 mg is superior to placebo:	Percentage of participants achieving body weight reduction $\geq 10\%$, $\geq 15\%$ and $\geq 20\%$ at 72 weeks	logistic model in Section 4.3.2.1 for treatment-regimen estimand and logistic model in Section 4.3.2.2 for efficacy estimand	
	Mean change in HbA1c (%) from randomization at 72 weeks	ANCOVA model in Section 4.3.2.1 for treatment-regimen estimand and MMRM model in Section 4.3.2.2 for efficacy estimand, with baseline HbA1c value to replace baseline body weight as an additional covariate.	LSM estimates will be plotted by treatment through 72 weeks.
	Percentage of participants achieving target value of HbA1c $< 7\%$, $\leq 6.5\%$ and $< 5.7\%$ at 72 weeks	logistic model in Section 4.3.2.1 for treatment-regimen estimand and logistic model in Section 4.3.2.2 for efficacy estimand, with baseline HbA1c value to replace baseline body weight as an additional covariate.	
	Mean change in waist circumference (cm) from randomization at 72 weeks	ANCOVA model in Section 4.3.2.1 for treatment-regimen estimand and MMRM model in Section 4.3.2.2 for efficacy estimand, with baseline waist circumference to replace baseline body weight as an additional covariate.	LSM estimates will be plotted by treatment through 72 weeks.
	Mean change in fasting glucose (mg/dL) from randomization at 72 weeks	ANCOVA model in Section 4.3.2.1 for treatment-regimen estimand and MMRM model in Section 4.3.2.2 for efficacy estimand	Baseline fasting glucose will be used a covariate and baseline HbA1c group ($\leq 8.5\%$, $> 8.5\%$) will be used as a fixed effect. LSM estimates will be plotted by treatment through 72 weeks.
Tirzepatide (all doses combined) is superior to placebo:	Mean change in triglycerides, HDL-cholesterol, and non-HDL-cholesterol from randomization at 72 weeks	ANCOVA model in Section 4.3.2.1 for treatment-regimen estimand and MMRM model in Section 4.3.2.2 for efficacy estimand, with baseline lipids value in place of baseline body weight as a covariate.	Estimated means will be plotted by treatment through 72 weeks. Log transformation will be adopted for lipid parameters.

Objectives	Relative to the efficacy measure:	Analysis conducted in a manner similar to	Additional Information
	Mean change in SBP (mmHg) from randomization at 72 weeks	ANCOVA model in Section 4.3.2.1 for treatment-regimen estimand and MMRM model in Section 4.3.2.2 for efficacy estimand, with baseline SBP in place of baseline body weight as a covariate.	LSM estimates will be plotted by treatment through 72-weeks.

Abbreviations: ANCOVA = analysis of covariance; HbA1c = hemoglobin A1c; HDL = high-density lipoprotein; LSM = least squares mean; MMRM = mixed model for repeated measures; SBP = systolic blood pressure.

Decision regarding reject/accept of the statistical hypothesis for each objective will be guided by the 2-sided p-values, and details are included in Section 2.1.

For submission of Study GPHL to the US FDA to support the registration of tirzepatide for chronic weight management, the key secondary efficacy assessment will be guided by the treatment regimen estimand, conducted using the same population as for the primary analysis. Assessment of the key secondary objectives will be conducted with hybrid imputation of missing data (see Section 4.3.2.3).

For other regulatory agencies, publications, and other purposes, the assessment of key secondary efficacy objectives may be guided by the efficacy estimand using the same population as for primary analysis.

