The sample size determination assumes that evaluation of superiority of tirzepatide 10 mg and tirzepatide 15 mg to placebo will be conducted in parallel, each at a 2-sided significance level of 0.025 using a 2-sample t-test. Additionally, a difference of at least 11% mean body weight percentage reduction from randomization at 72 weeks for tirzepatide 10 mg and/or tirzepatide 15 mg compared to placebo, a common SD of 10%, and a dropout rate of 25% are assumed for statistical power calculations. Under the assumptions above, randomizing 900 participants in a 1:1:1 ratio to tirzepatide 10 mg (300), tirzepatide 15 mg (300), and placebo (300) provides more than 90% power to demonstrate superiority of each tirzepatide dose to placebo.

The chosen sample size and randomization ratio also provides >90% power to establish superiority of 10-mg tirzepatide and 15-mg tirzepatide dose to placebo in terms of proportion of participants achieving at least 5% body weight reduction at 72 weeks, conducted in parallel using a Chi-square test, each at a 2-sided significance level of 0.025, assuming 25% placebo treated participants and 90% tirzepatide-treated participants achieving the goal and a dropout rate of 25%.

6. Supporting Documentation

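### SAP 4.4.1 tests two sparse key secondary responder endpoints (at least 20% weight loss, HbA1c below 5.7%) by logistic regression without naming a test that survives an empty placebo cell

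*SAP*

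**What the plan says.** SAP section 2 lists at least 20% weight loss (H15,4 and H10,4) and HbA1c below 5.7% (H15,9 and H10,9) among the type-I-controlled hypotheses. Section 4.9 records that the first was added and the second promoted from additional secondary. Table GPHL.4.2 in section 4.4.1 assigns both to the "logistic model in Section 4.3.2.1 for treatment-regimen estimand and logistic model in Section 4.3.2.2 for efficacy estimand", with baseline HbA1c as the covariate for the HbA1c targets. Below the table: "Decision regarding reject/accept of the statistical hypothesis for each objective will be guided by the 2-sided p-values".

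Sections 4.3.2.1 and 4.3.2.2 describe these fits only as logistic regression; neither the estimator nor the test statistic is named. For the treatment-regimen estimand, missing values are multiply imputed and then dichotomised. For the efficacy estimand, each missing value is replaced by its MMRM prediction and then dichotomised.

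Fallbacks for model failure exist for the MMRM covariance structure (4.3.2.2) and for the retrieved-dropout imputation (4.3.2.3), but not for the logistic model. Section 4.1 keeps Fisher's exact test for comparisons that need no covariate adjustment. It also allows an analysis to be omitted when events are few, which does not say how a controlled hypothesis would then be decided. The risk-difference analysis in section 4.5 is exploratory, optional and limited to weight thresholds.

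**The concern.** These are the responder thresholds that placebo participants are least likely to reach. If no placebo participant responds, the maximum-likelihood log odds ratio is infinite. The software then reports whatever estimate and standard error it held when it stopped, and the Wald ratio of the two tends to zero. The strongest possible separation of the arms is thus reported as no evidence of a difference. Multiple imputation adds exposure, because Rubin's rules average the variances and one degenerate fit can dominate the average.

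At stake is a key secondary hypothesis that is not rejected for a computational reason, or a rescue test chosen after the data are seen.

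**Working it through.** **1. The plan's own power figure.** SAP section 5 gives "a difference of at least 11% mean body weight percentage reduction from randomization at 72 weeks", "a common SD of 10%, and a dropout rate of 25% are assumed for statistical power calculations", 300 per arm and two-sided 0.025 per dose. Completers: 300 × 0.75 = 225 per arm. The t-test noncentrality is (11/10) × √(225/2) = 11.7 against a critical value of about 2.25, so power exceeds 99.9%. For 25% against 90% by chi-square, power also exceeds 99.9%. The stated figure of more than 90% is correct, but it says nothing about the sparse endpoints, for which no rates are given.

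**2. How likely is an empty placebo cell at 20%?** Assume normal percent weight change with 25% of placebo at or below −5%. Then placebo mean = −5 + 0.6745 × SD, p = Φ((−20 − mean)/SD), and the chance of none is (1 − p)^300.

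| SD | Mean | p | Expected of 300 | Chance of none |
|---|---|---|---|---|
| 10 (SAP) | +1.74 | 1.48% | 4.5 | 1% |
| 8 (assumed) | +0.40 | 0.54% | 1.6 | 20% |
| 7 (assumed) | −0.28 | 0.24% | 0.7 | 48% |

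For HbA1c below 5.7% no such calculation is possible. Protocol 5.1 requires screening HbA1c of 7% to 10%, which makes placebo responders plausibly rare, but neither document gives a Week 72 placebo mean, SD or rate.

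**3. What the test returns.** Active counts are illustrative, with 300 per arm and maximum likelihood run to 25 iterations.

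| Placebo | Active | Wald p | Likelihood-ratio p | Fisher p |
|---|---|---|---|---|
| 0 | 25 | 0.999 | 2e-9 | 4e-8 |
| 0 | 60 | 0.999 | 2e-21 to 3e-21 | 7e-20 |
| 1 | 60 | 2e-5 | | |
| 3 | 60 | 8e-8 | | |

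With 0 against 60, the fitted log odds ratio is about 25 with a standard error of about 28,000. Adding sex, antihyperglycemic type, country and a baseline covariate does not change this. The failure belongs to the empty cell: a single placebo responder restores a small p.

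**4. Pooling over imputations.** Rubin's total variance is T = Ū + (1 + 1/m)B. Take m = 100 and 60/300 active, with 1 or 2 placebo responders in each data set: pooled log odds ratio 3.97, SE 0.95, p = 3e-5. Make one data set empty in the placebo arm. Its standard error alone contributes 28,270/√100 = 2,827 to the pooled SE. The pooled log odds ratio is about 4.2, so z = 4.2/2,827 = 0.0015 and p = 0.999. A comparable run gave 0.997; the last digits reflect where the iterations stop.

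The stopping point matters more generally. Stopping the degenerate fit at 8, 10 or 15 iterations gives it an SE of about 5.8, 15.6 or 190. Pooled p is then about 6e-4, 0.04 or 0.83. The decision would rest on a software setting.

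**5. Does Firth repair it?** Penalised likelihood-ratio tests with 0/300 placebo give p = 2e-20, 3e-10 and 2e-5 at 60, 30 and 15 active responders. For pooling, the two-arm Firth estimate without covariates equals the log odds ratio after adding 0.5 to each cell. At 0 against 60 it is ln[(60.5 × 300.5)/(240.5 × 0.5)] = 5.02. With fitted rates 0.5/301 and 60.5/301, the SE is √(1/0.498 + 1/48.2) = 1.43, so both are finite. Repeating step 4 with Firth fits gives pooled p = 4e-6 with no empty data set and 6e-6 with one.

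**The case against.** The strongest reply is that the SAP does not specify a Wald test. It says logistic regression and leaves the statistic open, and a likelihood-ratio test on the same fit stays highly significant. That stands: the defect is under-specification, and a reader who concludes that the SAP chose a failing test goes further than its text. It helps less for the treatment-regimen estimand. Section 4.3.2.1 cites Rubin's method for the ANCOVA, and the same pooling of estimates and standard errors is the natural reading for the logistic model; that pooling is Wald-type.

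The second reply is that the event is improbable. At the SAP's stated SD of 10 it is, at about 1%. A reader might combine "assuming 25% placebo treated participants and 90% tirzepatide-treated participants achieving the goal" with an 11-point difference and infer an SD near 5.6, hence an 88% chance of no placebo responder. The documents do not support that. They state SD 10, and they give 11 points as a minimum. The 25% and 90% rates fit SD 10 equally well with a difference of 10 × (1.2816 + 0.6745) = 19.6 points, or SD 8 with 15.6. The responder calculation does not assume normality.

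Third, under the treatment-regimen estimand the full analysis set keeps data after glycemic rescue, which makes low placebo HbA1c values less rare. This also stands, and no HbA1c probability is claimed here.

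**Conclusion.** The gap is real and worth closing. Two type-I-controlled endpoints rest on a model whose default inference fails when the placebo cell is empty, and no fallback is stated. If that happens, p moves from far below any plausible threshold to near 1. For the treatment-regimen estimand, a single empty imputed data set can be enough when the fit is iterated close to its limit. The chance of an empty cell at 20% weight loss is about 1% at the SAP's SD and 20% to 48% at assumed SDs of 8 and 7, all under normality and 25% placebo responders at the 5% threshold. For HbA1c below 5.7% it is unknown.

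The error is lost power. There is no type I inflation, and the co-primary comparisons are unaffected at their planned rates. A reader might infer that a failed test would block later hypotheses. That depends on Figure GPHL.2.1, which is not shown in the text reviewed, so it cannot be judged.

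**What to change.** Before unblinding, add to SAP 4.3.2.1 and 4.3.2.2 that the comparisons for at least 20% weight loss and HbA1c below 5.7% use Firth penalised logistic regression with the same covariates, in all imputed data sets. For the treatment-regimen estimand, pool the Firth log odds ratios and standard errors by Rubin's rules. For the singly imputed efficacy-estimand analysis, take the p-value and confidence interval from the penalised profile likelihood.

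An alternative is a trigger for any responder comparison with a low fixed count in an arm, such as fewer than 5, in the observed or any imputed data set. Naming the two endpoints outright is simpler. At SD 10 the placebo count would be below 5 about 54% of the time (binomial, 300 and 1.48%), and a trigger of 10 would fire about 98% of the time.

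The cost is a few SAP sentences, a model option and an odds ratio slightly shrunk towards 1. Pooled Firth inference is still Wald-type and so conservative: if every imputed data set has no placebo responder, the formula in step 5 of the working gives p of about 4e-4, 0.005 and 0.016 at 60, 25 and 15 active responders. That is weaker than the profile-likelihood result, but it no longer depends on where an iteration stops.

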6.3. Measures to Minimize Bias: Randomization and Blinding

This is a double-blind, randomized study.

Participants who meet all criteria for enrollment will be randomized to 1 of the study treatment groups at Visit 3. Assignment to treatment groups will be determined by a computer-generated random sequence using an IWRS. Participants will be randomized in a 1:1:1 ratio to receive tirzepatide 10 mg, tirzepatide 15 mg, or placebo.

The randomization will be stratified by country, sex (female, male), and type of AHM used at randomization (classified according to its potential effect on body weight, see table below).

Stratification Based on the Use of Antihyperglycemic Medications

Stratum	Potential Body Weight Effect	Participants to be Included in the Corresponding Stratum
1	Significant weight loss	
 • The use of an SGLT-2 inhibitor alone or in combination with any other AHMs except for an SU or TZD
2	Significant weight gain	
 • The use of an SU alone or in combination with any other AHMs except for an SGLT-2 inhibitor OR 
 • The use of a TZD alone or in combination with any other AHMs except for an SGLT-2 inhibitor
3	Weight neutral and others	
 • Lifestyle management only: no background AHMs OR 
 • Metformin monotherapy OR 
 • The use of an SGLT-2 inhibitor in combination with an SU and/or TZD, with or without other AHMs Note: The body weight effect of SGLT-2 inhibitor may be offset

Stratum	Potential Body Weight Effect	Participants to be Included in the Corresponding Stratum
		
by SU/TZD, and vice-versa, when used in combination.
 
OR
 
 • All other monotherapy (such as glinides and AGIs) or combination therapy which does not fall under stratum 1 or 2

Abbreviations: AGI = alpha-glucosidase inhibitor; AHM = antihyperglycemic medication; SGLT = sodium-glucose cotransporter; SU = sulfonylurea; TZD = thiazolidinedione.

Investigators, site staff, clinical monitors, and participants will remain blinded to the treatment assignments until the study is complete.

Emergency unblinding may be performed through the IWRS. This option may be used ONLY if the participant's well-being requires knowledge of the participant's treatment assignment. All unblinding events are recorded and reported by the IWRS.

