1	9-Sep-2022	Not Applicable	Original version
2	See date on page 1	See below summary	See below summary

The key changes of SAP Version 2 are summarized below:

1. Added mean change in EQ-5D-5L utility score and VAS score to “Additional Secondary objectives, by dose analysis” in [Table GPHL.1.1](#) and Section [4.9](#) to align with analyses described in [Table GPHL.4.3](#) (see Section [1.1.1](#)).
2. In response to US FDA feedback, clarified that the population-level summary for the “difference in response percentages between treatment conditions” is assessed by odds ratio (see Section [1.1.2.1](#)).
3. Clarified that placebo multiple imputation will be used for missing data imputation in Category 1 for treatment-regimen estimand if there are not enough retrieved dropouts to impute missing data in Category 2 (see Section [4.3.2.3](#)).
4. In response to US FDA feedback, added sensitivity analyses to evaluate the robustness of the primary efficacy results using different missing data imputation methods (see Section [4.3.2.4](#)).
5. Updated to use “baseline HbA1c value” rather than “baseline HbA1c group ($\leq 8.5\%$, $>8.5\%$)” as a covariate in analysis models for efficacy measures related to HbA1c to better adjust for baseline HbA1c information (see Section [4.4.1](#)).
6. Added exploratory endpoints to assess risk difference among each tirzepatide dose and placebo arm for an unconditional effect in proportions of participants achieving body weight reduction targets (see Section [4.5](#)).

1. Introduction

Changes to the protocol-planned analyses are described in Section 4.9.

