- $H_{15,2}$ and $H_{10,2}$: superiority of tirzepatide 10 mg and/or 15 mg versus placebo for percentage of participants who achieve $\geq 10\%$ body weight reduction from randomization at 72 weeks
- $H_{15,3}$ and $H_{10,3}$: superiority of tirzepatide 10 mg and/or 15 mg versus placebo for percentage of participants who achieve $\geq 15\%$ body weight reduction from randomization at 72 weeks
- $H_{15,4}$ and $H_{10,4}$: superiority of tirzepatide 10 mg and/or 15 mg versus placebo for percentage of participants who achieve $\geq 20\%$ body weight reduction from randomization at 72 weeks
- $H_{15,5}$ and $H_{10,5}$: superiority of tirzepatide 10 mg and/or 15 mg versus placebo for change from randomization in waist circumference (cm) at 72 weeks
- $H_{15,6}$ and $H_{10,6}$: superiority of tirzepatide 10 mg and/or 15 mg versus placebo for change from randomization in HbA1c (%) at 72 weeks
- $H_{15,7}$ and $H_{10,7}$: superiority of tirzepatide 10 mg and/or 15 mg versus placebo for percentage of participants who achieve HbA1c $< 7\%$ at 72 weeks
- $H_{15,8}$ and $H_{10,8}$: superiority of tirzepatide 10 mg and/or 15 mg versus placebo for percentage of participants who achieve HbA1c $\leq 6.5\%$ at 72 weeks
- $H_{15,9}$ and $H_{10,9}$: superiority of tirzepatide 10 mg and/or 15 mg versus placebo for percentage of participants who achieve HbA1c $< 5.7\%$ at 72 weeks
- $H_{15,10}$ and $H_{10,10}$: superiority of tirzepatide 10 mg and/or 15 mg versus placebo for change from randomization in fasting glucose at 72 weeks
- $H_{p,11}$: superiority of tirzepatide (all doses combined) versus placebo for change in SBP (mmHg) from randomization at 72 weeks
- $H_{p,12}$: superiority of tirzepatide (all doses combined) versus placebo for change in triglycerides (mg/dL) from randomization at 72 weeks
- $H_{p,13}$: superiority of tirzepatide (all doses combined) versus placebo for change in non-HDL-cholesterol (mg/dL) from randomization at 72 weeks
- $H_{p,14}$: superiority of tirzepatide (all doses combined) versus placebo for change in HDL-cholesterol (mg/dL) from randomization at 72 weeks

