2.1. Multiplicity Adjustment

For primary and key secondary efficacy objectives, the details of type I error control strategy are illustrated in [Figure GPHL.2.1](#). Both efficacy estimand and treatment regimen estimand will be used to assess these objectives. As they are intended for different purposes, no multiplicity adjustments will be made for conducting separate analyses relative to the efficacy and treatment regimen estimands. In addition, no multiplicity adjustments will be made for evaluating other secondary and exploratory objectives, or for safety assessments.

Abbreviations: FG = fasting glucose; H = hypothesis; HbA1c = hemoglobin A1c; HDL-C = high-density lipoprotein cholesterol; Non-HDL-C = non high-density lipoprotein cholesterol; p = pooled dose; SBP = systolic blood pressure; WC = waist circumference; WL = weight loss.

Figure GPHL.2.1. Type 1 error control strategy for primary and key secondary efficacy endpoints.

3. Analysis Sets

For purposes of analysis, the following populations are defined:

Table GPHL.3.1. Description of Analysis Datasets

Population	Description
Entered	All participants who sign informed consent
Randomized	All participants who are randomly assigned a study drug.
Modified Intent-to-Treat (mITT)	All randomly assigned participants who are exposed to at least 1 dose of study drug. Participants will be included in the treatment group to which they were randomized.
Efficacy Analysis Set (EAS)	For glycemic control related endpoints: Data obtained during treatment period from mITT, excluding data after initiation of rescue antihyperglycemic medication or premature discontinuation of study drug (last dose date + 7 days). For other endpoints: Data obtained during treatment period from mITT, excluding data after premature discontinuation of study drug (last dose date + 7 days).
Full Analysis Set (FAS)	Data obtained during treatment period from mITT, regardless of adherence to study drug or initiation of rescue antihyperglycemic medication.
Safety Analysis Set (SS)	Data obtained during the treatment period plus safety follow-up period from mITT, regardless of adherence to study drug or initiation of rescue antihyperglycemic medication.

Unless otherwise specified, for analyses guided by the treatment regimen estimand, the FAS will be used; for analyses guided by the efficacy estimand, the EAS will be used; for safety analysis, the SS will be used.

4. Statistical Analyses

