4.4.2.1. Additional Secondary Efficacy Analyses

Table GPHL.4.3. Secondary Measures (Not Controlled for Type 1 Error)

Objective	Relative to the efficacy measure:	Analysis conducted in a manner similar to:	Additional Information
compare tirzepatide 10 mg and/or 15 mg QW with placebo at 72 weeks:	Mean change in body weight (kg) from randomization	MMRM model in Section 4.3.2.2	LSM estimates through 72 weeks will be plotted by study treatment.
	Mean change in BMI (kg/m ²) from randomization	MMRM model in Section 4.3.2.2	Baseline BMI (kg/m ²) will be used as a covariate. LSM estimates through 72 weeks will be plotted by study treatment.

Objective	Relative to the efficacy measure:	Analysis conducted in a manner similar to:	Additional Information
	Mean change in 7-point SMBG from randomization	MMRM model in Section 4.3.2.2	Baseline SMBG value will be used as a covariate and baseline HbA1c group ($\leq 8.5\%$, $> 8.5\%$) will be used as a fixed effect. In addition to the analyses on each of the 7-points, similar analyses will be done for the 2-hour morning, midday, and evening meal excursions, the mean of all meals 2-hour excursion, the mean of all 7-point measurements, the mean of all pre-meal measurements, and the mean of all 2-hour postprandial measurements.
	Mean change in fasting insulin from randomization	MMRM model in Section 4.3.2.2	Baseline fasting insulin will be used as a covariate. Estimated means through 72 weeks will be plotted by study treatment. Log transformation will be adopted for fasting insulin.
	Mean change in IWQOL-Lite-CT Physical Function composite (PF) score from randomization	ANCOVA model	Terms of treatment, stratification factors, and baseline IWQOL-Lite CT PF score will be used as a covariate. Missing data will be imputed using LOCF method.
	Mean change in SF-36v2 acute form physical functioning domain (PF) score from randomization	ANCOVA model	Same as above but using baseline SF-36 v2 acute PF score as a covariate.
	Mean change in EQ-5D-5L utility score and VAS score from randomization	ANCOVA model	Same as above but using baseline EQ-5D-5L utility score and VAS score as a covariate, respectively.
compare tirzepatide QW (all doses combined) with placebo at 72 weeks	Mean change in DBP (mmHg)	MMRM model in Section 4.3.2.2	All tirzepatide doses will be pooled together. LSM estimates through 72 weeks will be plotted by study treatment.

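### Fasting glucose and 7-point SMBG models adjust for baseline HbA1c cut at 8.5%, where the continuous value used in the HbA1c models would be slightly more precise

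*SAP*

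**What the plan says.** Item 5 of the key changes in the SAP Version History replaces the two-level baseline HbA1c group (split at 8.5%) with the measured value, "as a covariate in analysis models for efficacy measures related to HbA1c to better adjust for baseline HbA1c information", and points to Section 4.4.1. In Table GPHL.4.2 of that section, the rows for HbA1c change and for the HbA1c targets follow this: "with baseline HbA1c value to replace baseline body weight as an additional covariate".

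The fasting glucose row of the same table reads "Baseline fasting glucose will be used a covariate and baseline HbA1c group", with the group entered as a fixed effect. The 7-point SMBG row of Table GPHL.4.3 (SAP 4.4.2.1) is built the same way: "Baseline SMBG value will be used as a covariate and baseline HbA1c group". The SAP gives no reason for keeping the group in these two rows.

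The two endpoints differ in status. Fasting glucose is a numbered hypothesis for each dose in SAP Section 2 (superiority "versus placebo for change from randomization in fasting glucose at 72 weeks"). SMBG is an additional secondary endpoint, and SAP 2.1 says "no multiplicity adjustments will be made for evaluating other secondary and exploratory objectives".

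On the design, Protocol 6.3 states: "The randomization will be stratified by country, sex (female, male), and type of AHM used at randomization". HbA1c is not among the strata. As a cut of baseline HbA1c, 8.5% otherwise appears only in the subgroup lists (Protocol 9.4.7.2, SAP 4.7.2.1).

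**The concern.** The sponsor's reason for item 5 is that the continuous value carries more baseline information than the two-level group. That holds wherever baseline HbA1c is used as an adjuster, including these two rows. Entry requires a screening HbA1c between 7% and 10% (Protocol 5.1), so 8.5% is the middle of the eligible range. The fasting glucose model therefore treats participants at 7.0% and 8.5% as alike, and those at 8.6% and 10% as alike. An analysis that must respect a stratified randomization would have a reason to keep a category, but HbA1c is not a stratum.

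What is at stake is a little precision on one controlled endpoint and one uncontrolled one, together with a consistent adjustment rule across the glycemic endpoints.

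**Working it through.** **The plan's own figure.** The documents state no power, SD or correlation for fasting glucose or SMBG. The only stated power is above 90% for the co-primary endpoints (SAP Section 5), "each at a 2-sided significance level of 0.025 using a 2-sample t-test". With 300 × 0.75 = 225 completers per arm, a difference of 11 and an SD of 10, the test statistic is centred at 1.1 × √(225/2) = 11.67, against a critical value of 2.24. Power is above 99.9%. It is also above 99.9% for 90% versus 25% responders. The stated figure is confirmed, and nothing below changes it.

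**Formula.** Let Y be Week 72 glucose, F baseline glucose, H baseline HbA1c, G the indicator of H above 8.5%, and k the correlation of H with G. Given F, the partial correlation of Y with H is

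p_c = (r_YH − r_YF·r_FH) / √[(1 − r_YF²)(1 − r_FH²)].

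For the group, p_g has the same form with k·r_YH and k·r_FH in place of r_YH and r_FH. Replacing G by H lowers residual variance by the fraction (p_c² − p_g²)/(1 − p_g²).

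**One case worked.** Assume HbA1c is normal with 30% above the cut. Then k² = 0.348²/(0.3 × 0.7) = 0.576 and k = 0.759. Take r_YF = r_YH = 0.4 and r_FH = 0.5.
- p_c = 0.2/√(0.84 × 0.75) = 0.252
- p_g = (0.304 − 0.4 × 0.379)/√(0.84 × 0.856) = 0.179
- Fall = (0.0635 − 0.0320)/(1 − 0.0320) = 3.3%

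**Effect of the entry range.** Limiting HbA1c to 7-10% shrinks its spread. The last column comes from simulation with HbA1c of mean 8 and SD 0.9, and with correlations set before truncation. All correlations are assumptions, and r_FH runs from 0.5 to 0.7.

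| Assumed predictor strength | r_YF | r_YH | Fall, no entry limit | Fall, HbA1c 7-10% |
|---|---|---|---|---|
| Glucose stronger | 0.4-0.5 | 0.3-0.4 | 0.05-0.8% (0.4 vs 0.3 only) | 0.03-1.1% |
| Equal | 0.3 or 0.4 | same | 1-3% | 0.6-1.7% |
| HbA1c somewhat stronger | 0.3 | 0.4 | about 5% | about 2.6% |
| HbA1c clearly stronger | 0.3 | 0.5 | 10-12% | 5.1-6.7% |

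In standard error terms, 2.6% of variance is 1 − √0.974 = 1.3%, and 6.7% is 1 − √0.933 = 3.4%.

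**Second route.** Here the partial correlation of HbA1c with the outcome is fixed directly at 0.1 to 0.3, and r_FH runs from 0.4 to 0.8. With HbA1c truncated normal on 7-10%, the variance ratio of group to continuous is 1.0037 to 1.0579, a fall of 0.4% to 1 − 1/1.0579 = 5.5%. At a partial correlation of 0.2 it is 1.5% to 2.3%. Adding a uniform and an untruncated normal distribution widens the ratio to 1.003-1.067.

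Starting from an assumed 80% power at an assumed local alpha of 0.025, power becomes Φ[(2.241 + 0.842)·√ratio − 2.241], or 80.1% to 82.7%.

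**Validity.** In 4,000 simulated null trials with 225 per arm, the group-adjusted ANCOVA rejected at a rate of 0.0225 against a nominal 0.025 (Monte Carlo standard error 0.0025). There is no sign of inflation.

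**The case against.** The strongest reply is that HbA1c plays a different role in the two sets of models. In the HbA1c models it is the outcome's own baseline, so a two-level group adjusted the endpoint only coarsely for itself, and item 5 repaired that. The fasting glucose and SMBG models already contain their own baseline as a covariate, and HbA1c is a second adjuster. This stands, and it is why the gain is small.

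Three further points also stand:
- Waist circumference, lipids and SBP are adjusted only for their own baseline plus the common terms. By the SAP's usual standard, fasting glucose is not under-adjusted.
- A two-level factor does not assume a linear HbA1c effect. The continuous term does, and so does every calculation above.
- Changing the model of a controlled endpoint means a further SAP version and some reprogramming.

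None of these gives a reason to prefer the 8.5% cut, and the SAP offers none.

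A reader might infer that item 5 was only half carried out and that the SAP contradicts itself. The text does not support this: item 5 is limited to measures related to HbA1c, and leaving fasting glucose and SMBG unchanged is consistent with that wording. Whether it was deliberate or an oversight, the documents do not say. A reader might also infer that the fasting glucose test is unsound. It is prespecified, and the simulation shows no inflation.

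**Conclusion.** The point holds as a small, low-priority improvement. Two glycemic rows keep a cut that the sponsor gave up in the HbA1c rows for the sake of better adjustment, and the randomization does not call for it.

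The expected fall in residual variance is roughly 0-3%, or about 5-7% if baseline HbA1c is clearly the better predictor of Week 72 glucose. Figures of 10-12% are tempting, but they need that same favourable assumption and also ignore the 7-10% entry range. Nothing in the documents supports the assumption.

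These sizes rest on assumed correlations, an assumed HbA1c distribution and a linear effect. The entry range applies to screening, and HbA1c is measured again at randomization, so some baseline values may lie outside 7-10%; the truncation is therefore approximate. The local alpha for fasting glucose is in a figure that is not shown, so 0.025 was assumed. No stated sample size, power or alpha changes. For SMBG, which is outside type I error control, the matter is one of consistency.

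**What to change.** Before unblinding, replace the two-level baseline HbA1c group with the baseline HbA1c value, as a continuous covariate, in the fasting glucose row of SAP Table GPHL.4.2 and the 7-point SMBG row of Table GPHL.4.3. Keep the endpoint's own baseline in each model, and keep the 8.5% group for the subgroup analyses only.

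The cost is a minor SAP revision, a change to the model code, and acceptance of a linear HbA1c effect. No new data are needed. If the group is kept on purpose, one sentence giving the reason would be a sufficient answer.
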